# Table 2–3Assumptions, marginal power and effective power for each confirmatory
endpoint in the hierarchical testing procedure given an anticipated number of
282 randomised subjects

	Assumed mea proportion fo liraglutide 3.0	n (±SD) / r completers ) mg placebo	Expected mean (±SD) / proportion for liraglutide 3.0 mg #	Expected difference #	Marginal power (%)	Effective power (%)
% weight change	-9.0 (±7.0)	-4.0 (±7.0)	-7.5 (±7.4)	-3.5	98.3	98.3
5% responders	72%	44%	63%	19%	90.0	88.5
10% responders	44%	20%	37%	17%	90.3	79.9
15% responders	20%	6%	15%	9%	75.0	59.9
4% responders at week 16	70%	45%	63%	18%	84.2	50.4
WC change	-9.0 (±7.0)	-5.0 (±7.0)	-7.8 (±7.2)	-2.8	90.8	45.8
SF-36 PF	3.7 (±8.0)	2.4 (±8.0)	3.3 (±8.0)	0.9	15.8	7.2
IWQoL-Lite for CT PF	16.0 (±18.0)	11.0 (±18.0)	14.5 (±18.1)	3.5	36.7	2.7
6MWT change	8.2 (±12.0)	5.8 (±12.0)	7.5 (±12.1)	1.7	21.5	0.6

SD standard deviation, WC waist circumference, SF-36 PF Short Form-36 v2.0 acute physical functioning score, IWQoL-Lite for CT PF Impact of Weight on Quality of Life-Lite for Clinical Trial Version Physical function domain (5- items) score, 6MWT six minute walking distance test;

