#### 2.1 Sample size calculation

The sample size calculation is based on the analysis approach addressing the primary estimand for the primary endpoints change in body weight (%) from baseline to week 56 (% weight change) and proportion of subjects losing  $\geq$  5% of baseline body weight at week 56 (5% responders).

The two primary endpoints will be tested in a hierarchical order.

The study design is a 1:1 randomisation with 282 subjects in total (141 subjects in each arm). Please see Table 2–2 for general specifications on sample size and power calculation.

 Table 2–2
 General specifications for sample size and power calculation

Endpoint	Statistical test	Minimum required power (%)
% weight change	Two-group Satterthwaite unpooled t test	90.0 (marginal)
	on the mean difference with $\alpha = 0.05$	
	assuming unequal variances	
5% responders	Pearson chi-square test for two	90.0 (marginal)
	independent proportions with $\alpha$ =0.05	

 $\boldsymbol{\alpha} {:} \text{ two-sided significance level}$ 

In the following paragraphs treatment differences and standard deviations (SD) are given without units.

Statistical Analysis Plan		Date:	07 July 2018	Novo Nordisk
Trial ID: NN8022-4274	CONFIDENTIAL	Version:	1.0	
UTN: U1111-1177-5059	CONFIDENTIAL	Status:	Final	
EudraCT No.: 2015-005592-24		Page:	9 of 24	

Body weight measurements from returning discontinuing subjects will be used in the primary analysis. But for the sample size calculations, it is assumed that all subjects who discontinue will not return at week 56 and that they have a % weight change like placebo subjects who completed the trial. It is expected that % weight change for liraglutide 3.0 mg subjects who discontinue might be somewhere in between completing placebo subjects and completing liraglutide 3.0 mg subjects. The assumption is thus expected to lead to a conservative effect estimate. In trial NN8022-1839 in non-diabetic subjects and with obesity, around 31% treatment discontinuations were observed in the placebo group, around 25% in the liraglutide 3.0 mg group. The calculated sample size ensures adequate power if the proportion of discontinuing subjects should be as high as 30%.

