Based on findings from NN8022-1839, a difference in % weight change between liraglutide 3.0 mg and placebo of -5 (-9% vs. -4%, SD=7) is assumed among completing subjects. For sample size calculation, a common SD of 7 was assumed for completers of liraglutide 3.0 mg or placebo. In NN8022-1839, a SD of 6.65 was seen for % weight change among subjects completing liraglutide 3.0 mg at week 56; 5.88 was observed among subjects completing placebo. Adjusting for 30% discontinuation and using a mixture distribution, a difference of -3.5 is expected in the primary analysis. A sample size of 282 subjects (141 in each arm), gives a marginal power of 98.3%.

For the primary endpoint 5% responders, the expected proportions were calculated based on the same assumptions as above. Adjusting for 30% discontinuation gives an expected 5% responders proportion of 63% in the liraglutide 3.0 mg arm and 44% in the placebo arm. With 282 subjects, this results in a marginal power of 90%.

Given these assumptions, the sample size of 282 subjects (141 in each arm), results in a combined power of 88.5%.

The tests of superiority of liraglutide 3.0 mg to placebo for each of the confirmatory endpoints are performed hierarchically in the order in which the endpoints are presented (see Sections 4.2.1 and 4.2.2.1 in the protocol). The two primary endpoints are included in the statistical testing hierarchy, and the primary objective will be met if superiority of liraglutide 3.0 mg vs. placebo is demonstrated for each of the primary endpoints. The test hierarchy is given in Table 2–3 with underlying assumptions, marginal power and effective power. The effective was calculated using a naïve and conservative approach, which assumes no correlation of endpoints by multiplying the respective marginal powers. Assumptions made to calculate the power for the two primary endpoints and all confirmatory secondary endpoints are also presented in Table 2–3.

Statistical Analysis Plan		Date:	07 July 2018	Novo Nordisk
Trial ID: NN8022-4274	CONFIDENTIAL	Version:	1.0	
UTN: U1111-1177-5059	CONFIDENTIAL	Status:	Final	
EudraCT No.: 2015-005592-24		Page:	10 of 24	

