#### 2.3.1.1 Statistical model for the primary endpoint % weight change

The primary endpoint % weight change will be analysed using analysis of covariance (ANCOVA) including the factors and covariates listed in Table 2-4.

Factors and covariates at baseline	Туре	Categories
Randomised treatment	Factor	Liraglutide 3.0 mg, placebo
Gender	Factor	Male, female
BMI (kg/m  )	Factor	[30,35[, [35,40[, ≥40
Body weight (kg)	Covariate	Not applicable

 Table 2–4
 Factors and covariates for the analysis of the primary endpoints

The factors and covariates will be included in the model as main effects in an additive structure. The estimated treatment difference between liraglutide 3.0 mg and placebo will be reported together with the associated two-sided 95% CI and corresponding p-value.

The superiority test of liraglutide 3.0 mg vs. placebo will be carried out as follows:

Let  $\mu_{\text{liraglutide}}$  and  $\mu_{\text{placebo}}$  denote the true mean of % weight change for liraglutide 3.0 mg and placebo group, respectively. The hypothesis and the alternative are:

 $H: \ \mu_{liraglutide} \geq \mu_{placebo} \ against \ the \ alternative \ H_A: \ \mu_{liraglutide} < \mu_{placebo}.$ 

The hypothesis will be rejected and superiority claimed, if the upper limit of the estimated twosided 95% CI of the treatment difference is below 0.

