#### Primary approach for handling of missing values

The primary approach for multiple imputations of missing values of body weight at week 56 (type MT+MD) for both the liraglutide 3.0 mg and placebo group is by sampling among all available assessments at week 56 in the placebo group (type AT+AD). This approach is also known as jump to reference and makes the assumption that subjects instantly after discontinuation lose any effect of randomised treatment beyond what can be expected from placebo treatment as adjunct to diet and exercise. Body weight measurements at visits between baseline and week 56 are not used for this imputation approach. The multiple imputation approach is done in three steps.

- **Imputation**: Step 1 defines an imputation model based on placebo subjects, which is used to impute missing body weight values at week 56 in both arms. This will be done 100 times and results in 100 complete data sets. A more detailed explanation of this step is given below.
- Analysis: Step 2 analyses each of the 100 complete data sets, using the statistical model defined in Section 2.3.1.1 and 2.3.1.2 and saves the 100 estimation results.

• **Pooling**: Step 3 integrates the 100 estimation results into a final result using Rubin's formula. The imputation model in step 1, uses placebo subjects from FAS with non-missing body weight measurements at baseline and week 56. The imputation model is a linear regression of body weight

Statistical Analysis Plan Trial ID: NN8022-4274 UTN: U1111-1177-5059 EudraCT No.: 2015-005592-24	CONFIDENTIAL	Date: Version: Status: Page:	07 July 2018 1.0 Final 13 of 24	Novo Nordisk
---	--------------	---------------------------------------	--	--------------

(kg) at week 56 on the factors and covariates listed in Table 2–4 (except randomised treatment) with no interactions. The estimated posterior distribution for the parameters (regression coefficients and variances) in the imputation model is then used to impute missing week 56 body weight values for both randomised treatment arms.

If 100 copies are not sufficient to establish stable results, a higher number will be used. The multiple imputations will be generated using Novo Nordisk trial number 80224274 as seed number.

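### The 75.0% power stated for 15% responders treats every week-56 weight as observed; in the plan's own no-return case the planned imputation analysis has about 67%

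*SAP*

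**What the plan says.** SAP 2.1 ties the sample size calculation to the analysis approach for the primary estimand. For planning, "it is assumed that all subjects who discontinue will not return at week 56", and discontinuers are given the weight change of placebo completers. The discontinuation rate is 30%, and it enters through a mixture distribution. For binary outcomes, Table 2-2 names one test, for 5% responders: "Pearson chi-square test for two" independent proportions, at two-sided 5%.

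The 15% responder row of Table 2-3 reads "15% responders 20% 6% 15% 9% 75.0 59.9": completer proportions, expected liraglutide proportion, difference, marginal power and effective power. Protocol Table 17-3 and the Amendment 1 version of it carry the same row.

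SAP 2.4.1 and Table 2-6 (test 4) send this endpoint through the primary imputation approach, followed by logistic regression with the terms of Table 2-4 ("Factors and covariates for the analysis of the primary endpoints"). SAP 2.3.2.2 defines that approach: missing values in both arms come from "sampling among all available assessments at week 56 in the placebo group", 100 times, and then "Step 3 integrates the 100 estimation results into a final result" by Rubin's formula.

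**The concern.** The adjustment for 30% discontinuation lowers the expected liraglutide proportion from 20% to 15%. It does not lower the information: the power formula still counts 141 observed outcomes per arm. If nobody returns, 30% of those outcomes do not exist and are drawn from a model fitted to the remaining placebo subjects. Rubin's formula then adds between-imputation variance, for which SAP 2.1 makes no allowance. A reader of Table 2-3 would take 75.0% as the power of the planned analysis in the stated planning case. At stake is the accuracy of a stated power for a confirmatory endpoint that sits above five later tests.

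**Working it through.** **Inputs from the SAP.** 141 per arm; two-sided 5%; completer means −9 and −4 with common SD 7; 30% discontinuation, placebo-like, none returning; 100 imputations. Normality of % weight change is an assumption, but it is the one that reproduces the table.

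**Step 1: reproduce 75.0%.**
- Placebo: Φ((−15+4)/7) = 0.0580. Liraglutide completers: Φ((−15+9)/7) = 0.1957.
- Liraglutide mixture: 0.7 × 0.1957 + 0.3 × 0.0580 = 0.1544. Difference: 0.0963.
- Pooled SE: √(2 × 0.1062 × 0.8938/141) = 0.0367. Unpooled SE: √((0.1544 × 0.8456 + 0.0580 × 0.9420)/141) = 0.0362.
- Power: Φ((0.0963 − 1.96 × 0.0367)/0.0362) = 74.98%.

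The printed, rounded 15% and 6% would give 69.5%, so the table used unrounded values and all 141 outcomes per arm. The same method gives 90.01% and 90.25% for 5% and 10% responders (stated 90.0 and 90.3).

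**Step 2: what no return implies.** 0.30 × 141 = 42.3, so about 42 missing values per arm and about 99 observed placebo subjects to fit the imputation model.

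**Step 3: the planned analysis without covariates.** Missing values were drawn 100 times from the placebo posterior predictive distribution, responder status derived, and log odds ratios pooled with T = Ū + (1 + 1/100)B. Power was 66.9% (20,004 trials, Monte Carlo SE 0.3 points); repeat simulations gave 66.0–68.1%. The between-imputation part is about 21% of total variance. Complete-data Wald logistic power is 74.7%, so the loss comes from imputation and not from replacing the chi-square test.

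**Step 4: with covariates.** The documents give no covariate distribution, so these inputs are assumed.
- Sex, BMI class and baseline weight simulated in both models (80% women; mean BMI 38 or 40; in one setting women lose 3 points more): 62.8–65.1%.
- Covariates explaining 0%, 10% or 20% of the variance of % weight change: 63.2%, 66.5%, 69.8%.

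**Step 5: if discontinuers return** (no covariates, placebo-like returners).

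| Share returning | 0% | 25% | 50% | 75% | 100% |
|---|---|---|---|---|---|
| Power | 66.9% | 69.2% | 71.7% | 73.7% | 74.5% |

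Other cases:
- half return, keeping 25% or 50% of the effect: 75.1% or 77.9%;
- the earlier trial's discontinuation (25% and 31%): 77.5% with half returning, 73.1% with none;
- the earlier trial's SDs (6.65 and 5.88), no return: 88.4%.

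**Step 6: the other imputed rows, no return.** The continuous rows use an assumed baseline R² of 0 to 0.3.

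| Row | Simulated | Stated |
|---|---|---|
| % weight change | 98.0–98.8% | 98.3% |
| 5% responders | 87.5–89.2% | 90.0% |
| 10% responders | 86.8–88.1% | 90.3% |
| Waist | 89.0–97.8% | 90.8% |
| SF-36 PF | 6–10% | 15.8% |
| IWQoL PF | 23–35% | 36.7% |
| 6MWT | 11–16% | 21.5% |

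**Step 7: effective power at test 4.** The stated product is 0.983 × 0.900 × 0.903 × 0.750 = 59.9%. Replacing only the last factor by 0.67 gives 53.5%. Simulated joint power for tests 1–4, which keeps the correlation between the weight endpoints, is about 59% without covariates and 55.7–58.6% with them.

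**The case against.** The simplification is visible: a chi-square test is named, the mixture is described, and Table 2-3 is footnoted as adjusted for discontinuation. The minimum power requirement covers only the two primary endpoints, and no sample-size or ordering decision rests on this row. This stands, and it limits the consequence. It does not make 75.0% the power of the planned analysis in the stated case.

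The plan also calls itself conservative. Liraglutide discontinuers "might be somewhere in between completing placebo subjects and completing liraglutide 3.0 mg subjects", so the expected effect may be understated, and SD 7 is larger than either SD seen earlier. These points stand for what may happen in practice, as Step 5 shows. They do not rescue the no-return case at SD 7: every missing value there is drawn from placebo, so how liraglutide discontinuers really fare does not enter the result. The other stated conservatism, that effective power "assumes no correlation of endpoints by multiplying the respective marginal powers", concerns the joint figure and not a marginal one.

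It is also fair that 67% comes from a model without covariates, which is not the planned one, and that the covariate range rests on assumed inputs. Both figures should therefore be given.

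A reader might infer that effective power at test 4 falls to 53.5%. That would mix one imputation-adjusted row with complete-data rows, and it lies further from the simulated joint power than the stated 59.9% does.

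**Conclusion.** The point holds for the plan's own planning case. With 30% discontinuing and none returning, 75.0% overstates the power of the planned analysis for 15% responders by about 8 points: about 67% without covariates, roughly 63–70% with them. This rests on normal % weight change, SD 7 and, for the range, assumed covariate inputs. It is not a forecast of the trial's actual power, which approaches 75% as placebo-like discontinuers return and can exceed it.

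Among the weight-loss endpoints the loss is material only here: about 1–3 points for 5% and 10% responders, none for % weight change. The SF-36, IWQoL and 6MWT rows are overstated for the same reason, but their stated effective power is already 7.2% or less.

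A reader might infer that the trial is too small. The documents do not support that. In the no-return case 5% responders fall nominally below the 90% minimum, to 87.5–89.2%, a shortfall of at most 2.5 points under a planning SD above both observed SDs. % weight change keeps its power. The matter is one of accurate reporting.

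**What to change.** In SAP Table 2-3, restate the 15% responder marginal power as about 67% (about 63–70% with covariates, inputs stated) for the no-return case. Add a footnote saying that:

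- the marginal powers of the imputed week-56 endpoints are complete-data figures that ignore between-imputation variance;
- among the weight-loss endpoints the loss is material only for 15% responders, with about 1–3 points for 5% and 10% responders and none for % weight change;
- the SF-36, IWQoL and 6MWT rows are overstated for the same reason.

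Do not rewrite the effective-power column from this row. Either recompute every imputed row on the same basis, or leave the column as the complete-data product and note that simulated joint power for tests 1–4 is about 59% without covariates (about 56–59% with them), close to the stated 59.9%. Test 5 is not affected, because missing week-16 weights count as non-response.

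The cost is one figure and one footnote, and a less favourable stated power. Sample size, test order and analysis stay as they are.

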# Adjusted for 30% discontinuation;

Assumptions are based on findings from NN8022-1839

#### 2.2 Definition of analysis sets

Two analysis sets are defined:

- The *full analysis set* (FAS) includes all randomised subjects according to the intention-to-treat (ITT) principle. Subjects in the FAS will be analysed as randomised.
- The *safety analysis set* includes all randomised subjects exposed to at least one dose of trial drug. Subjects will be analysed as treated.

Any observation excluded from the analysis database will be documented before database lock with the reason for exclusion provided.

#### 2.3 **Primary endpoints**

The two primary endpoints are as mentioned previously (see start of Section  $\underline{2}$ ):

- % weight change
- 5% responders

Statistical Analysis Plan Trial ID: NN8022-4274 UTN: U1111-1177-5059 EudraCT No.: 2015-005592-24	CONFIDENTIAL	Date: Version: Status: Page:	07 July 2018 1.0 Final 11 of 24	Novo Nordisk
---	---------------------	---------------------------------------	--	--------------

## 2.3.1 Analytical methods addressing the effectiveness estimand for the primary endpoints

These analyses will use the FAS. The analyses of the primary endpoints use baseline body weight and body weight at week 56, and assessments at week 56 may be missing ("missing on treatment [MT]" and "missing drop-outs [MD]"). First, a description of the statistical models for the primary endpoints is given under the assumption of no missing values (i.e. all subjects have body weight measurements at baseline and week 56). Subsequently, handling of missing data is described.

#### 2.3.1.1 Statistical model for the primary endpoint % weight change

The primary endpoint % weight change will be analysed using analysis of covariance (ANCOVA) including the factors and covariates listed in Table 2-4.

Factors and covariates at baseline	Туре	Categories
Randomised treatment	Factor	Liraglutide 3.0 mg, placebo
Gender	Factor	Male, female
BMI (kg/m  )	Factor	[30,35[, [35,40[, ≥40
Body weight (kg)	Covariate	Not applicable

 Table 2–4
 Factors and covariates for the analysis of the primary endpoints

The factors and covariates will be included in the model as main effects in an additive structure. The estimated treatment difference between liraglutide 3.0 mg and placebo will be reported together with the associated two-sided 95% CI and corresponding p-value.

The superiority test of liraglutide 3.0 mg vs. placebo will be carried out as follows:

Let  $\mu_{\text{liraglutide}}$  and  $\mu_{\text{placebo}}$  denote the true mean of % weight change for liraglutide 3.0 mg and placebo group, respectively. The hypothesis and the alternative are:

 $H: \ \mu_{liraglutide} \geq \mu_{placebo} \ against \ the \ alternative \ H_A: \ \mu_{liraglutide} < \mu_{placebo}.$ 

The hypothesis will be rejected and superiority claimed, if the upper limit of the estimated twosided 95% CI of the treatment difference is below 0.

#### 2.3.1.2 Statistical model for the primary endpoint 5% responders

This binary endpoint will be analysed using a logistic regression model. Factors and covariates will be those listed in Table 2–4. The estimated odds ratio (OR) between liraglutide 3.0 mg and placebo will be reported together with the associated two-sided 95% CI and corresponding p-value.

Statistical Analysis Plan Trial ID: NN8022-4274 UTN: U1111-1177-5059	CONFIDENTIAL	Date: Version: Status:	07 July 2018 1.0 Final	Novo Nordisk
EudraCT No.: 2015-005592-24		Page:	12 of 24	I

Let ORliraglutide/placebo denote the true odds ratio between liraglutide 3.0 mg and placebo. The hypothesis and the alternative are:

H:  $OR_{liraglutide/placebo} \le 1$  against the alternative  $H_A$ :  $OR_{liraglutide/placebo} > 1$ 

The hypothesis will be rejected and superiority claimed, if the lower limit of the estimated twosided 95% CI is above 1.

#### 2.3.2 Handling of missing values for the effectiveness estimand

#### 2.3.2.1 Handling of missing values at baseline

If an assessment has been made both at screening and randomisation, the value from the randomisation visit will be used as the baseline value. If the value measured at the randomisation visit is missing and the assessment has been made at screening, then the screening value will be used as the baseline value.

#### 2.3.2.2 Handling of missing values at week 56

Missing values at week 56 will be imputed and the relevant endpoints will be derived from the imputed values. Several approaches for imputation of missing values at week 56 will be applied. First, a description of the primary imputation approach used to address the effectiveness estimand for the primary endpoints is given. This is followed by a description of a number of sensitivity analyses.

#### Primary approach for handling of missing values

The primary approach for multiple imputations of missing values of body weight at week 56 (type MT+MD) for both the liraglutide 3.0 mg and placebo group is by sampling among all available assessments at week 56 in the placebo group (type AT+AD). This approach is also known as jump to reference and makes the assumption that subjects instantly after discontinuation lose any effect of randomised treatment beyond what can be expected from placebo treatment as adjunct to diet and exercise. Body weight measurements at visits between baseline and week 56 are not used for this imputation approach. The multiple imputation approach is done in three steps.

- **Imputation**: Step 1 defines an imputation model based on placebo subjects, which is used to impute missing body weight values at week 56 in both arms. This will be done 100 times and results in 100 complete data sets. A more detailed explanation of this step is given below.
- Analysis: Step 2 analyses each of the 100 complete data sets, using the statistical model defined in Section 2.3.1.1 and 2.3.1.2 and saves the 100 estimation results.

• **Pooling**: Step 3 integrates the 100 estimation results into a final result using Rubin's formula. The imputation model in step 1, uses placebo subjects from FAS with non-missing body weight measurements at baseline and week 56. The imputation model is a linear regression of body weight

Statistical Analysis Plan Trial ID: NN8022-4274 UTN: U1111-1177-5059 EudraCT No.: 2015-005592-24	CONFIDENTIAL	Date: Version: Status: Page:	07 July 2018 1.0 Final 13 of 24	Novo Nordisk
---	--------------	---------------------------------------	--	--------------

(kg) at week 56 on the factors and covariates listed in Table 2–4 (except randomised treatment) with no interactions. The estimated posterior distribution for the parameters (regression coefficients and variances) in the imputation model is then used to impute missing week 56 body weight values for both randomised treatment arms.

If 100 copies are not sufficient to establish stable results, a higher number will be used. The multiple imputations will be generated using Novo Nordisk trial number 80224274 as seed number.

